3.1.2 Missed visits

If any subjects are not attending, investigator will attempt all reasonable means to encourage to attend the study. However, any subjects not attending for two consecutive study visits are missed.

3.2 Visit conduct

3.2.1 Initial dispensing visit

The subject will receive a study summary form prior to enrolment and will then be required

to sign an informed consent form. When the subject has signed the consent form, they are considered to be enrolled on the study.

Subjects will be instructed on the following:

- 1. Lens handling, application and removal, where necessary.
- 2. Specific study instructions, such as the importance of not using any other contact lens products.
- 3. General contact lens information such as the management of red eyes.

The following procedures will be performed:

- 1. Details of the ocular history and contact lens wearing history of the subject.
- 2. Refraction and distance monocular logMAR visual acuity
- 3. Auto-keratometry measures using the Keratoraph 5M (Oculus, Germany)
- 4. Slit lamp biomicroscopy will be carried out for the signs of any abnormality using Efron Grading Scales.
- 5. The investigator will confirm that the subject satisfies all the inclusion and exclusion criteria. Subjects who fail to meet all the criteria at this time will be discontinued and replaced.
- 6. The study lenses will be fitted according to the randomisation order and allowed to settle for five minutes. The subject will be masked from the lens type.
- 7. Monocular logMAR visual acuity will be recorded before performing an overrefraction, and then monocular logMAR visual acuity will be carried out with the overrefraction in place.
- 8. Lens fit will then be assessed using the following evaluations: horizontal and vertical centration, corneal coverage and movement. Normally, for an acceptable fit, centration and movement will fall within currently accepted clinical criteria
- 9. The subject will then be discharged and asked to return for the one-week follow-up visit wearing the study lenses for a minimum of two hours. Subjects should be asked to wear their lenses for a minimum of eight hours per day, five days per week.

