2.1 Subject selection

Sixty subjects who are currently existing contact lenses wearers will be enrolled. Out of 60 subjects, twenty subjects will be recruited from the current wearers of 1.Day ACUVUE[®] DefineTM (Johnson & Johnson Vision Care Inc) and another twenty subjects will be current wearers of Claren 1-day Iris (Interrozzo Inc). Rest twenty subjects will be no previous wearer of any study lenses. All subjects will go through the screening procedure to ensure they satisfy the inclusion criteria. At the screening visit, a detailed Participant Information Sheet explaining the nature of the study will be provided to potential subjects along with a Participant Instruction Sheet, which includes study-specific instructions as well as general lens wear precautions. Once subject agrees to participate, then will be asked to sign a written consent form to confirm their agreement to participate the study.

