2.1.3 Inclusion criteria

Subjects will be only eligible for the study if they meeting the following inclusion criteria:

- 1. Age of 18 years and above and has full legal capacity as a volunteer
- 2. Understand the rights as a research subject and willing and able sign a statement of informed consent.
- 2. Existing soft contact lens wearers or previous experience of contact lens wear
- 3. Being able to wear the study lenses for at least eight hours a day
- 4. At least 6/9 visual acuity in each eye with the study lenses
- 5. Astigmatism less than 1.50 D in both eyes
- 5. Agreed to follow the protocol and not to participate in other clinical research for the duration of this study.

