2.1.4 Exclusion criteria

Subjects will not be eligible to take part in the study if they:

- 1. Have an ocular disorder which would normally contraindicate contact lens wear.
- 2. Have a systemic disorder or any infectious diseases which would normally contraindicate contact lens wear.
- 3. Have previously had any ocular surgery such as corneal refractive surgery
- 4. Have less than 6/9 visual acuity in each eye with the study lenses
- 5. Are currently using any topical medication such as eye drops or ointment.

6. Have any corneal distortion resulting from previous rigid lens wear or have keratoconus.

- 7. Are currently pregnant or lactating.
- 8. No previous contact lens wear

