3.1 Visit scheduling

Subjects will be required to attend for up to four visits –an initial dispensing visit, and three follow-up visits. Acceptable date ranges are shown in Table 3.

Visit	Target day to visit	Allowable range
Initial dispensing	NA	NA
One week	7 days from dispensing visit.	5-10 days from dispensing visit
Two week	7 days from dispensing visit.	5-10 days from dispensing visit
Three week	7 days from dispensing visit.	5-10 days from dispensing visit

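### Does it matter that 6/9 acuity in the study lenses is confirmed before any study lens has been fitted?

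*Combined protocol and SAP*

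**What the plan says.** Section 2.1.3 admits subjects with "At least 6/9 visual acuity in each eye with the study lenses". Section 2.1.4 gives the counterpart exclusion: "Have less than 6/9 visual acuity in each eye with the study lenses".

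Section 3.2.1 lists the steps of the dispensing visit. Ocular and lens history is step 1, and refraction with logMAR acuity is step 2. At step 5, "The investigator will confirm that the subject satisfies all the inclusion and exclusion criteria", and "Subjects who fail to meet all the criteria at this time will be discontinued and replaced". Step 6 follows: "The study lenses will be fitted according to the randomisation order and allowed to settle for five minutes". Acuity in that lens is recorded at step 7.

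Under section 3.2.2 the second pair goes on, and its acuity is read, at the end of the one-week visit (steps 9 and 10). Section 3.2.3 repeats those steps, which puts the third pair at the two-week visit.

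On screening, section 2.1 says "All subjects will go through the screening procedure to ensure they satisfy the inclusion criteria", and it also names a screening visit. The schedule in section 3.1 has no such visit: "Subjects will be required to attend for up to four visits", made up of one dispensing visit and three follow-ups. Section 2.1 recruits twenty current wearers of each comparator lens; of the others it says "Rest twenty subjects will be no previous wearer of any study lenses". Section 2.1.1 replaces enrolled subjects who do not complete the dispensing visit.

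**The concern.** A criterion about acuity in the lenses is applied at a point where the plan has not yet put a lens on the eye. Read literally, step 5 asks the investigator to certify something that cannot yet be measured.

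Staff might respond by applying the rule at step 7. Section 2.1.1 would still allow replacement then, because the dispensing visit is not complete. Whether a subject stayed in would depend partly on the lens that randomisation put first. Subjects who see poorly in a given lens would be removed only when they started on it, and a real difference in acuity between lenses could be understated. For the second and third lenses, sections 2.2, 2.5, 3.1.1 and 3.4 contain no acuity rule at all.

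**Working it through.** **The plan's own figure.** Section 1.5.1 gives effect size f = 0.20, α = 0.05, one group, m = 3 repetitions, correlation 0.5 and power 0.90. For a within-subject repeated-measures F test assuming sphericity, the noncentrality is λ = N·m·f²/(1 − correlation), with m − 1 and (N − 1)(m − 1) degrees of freedom.

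- N = 55: λ = 55 × 3 × 0.04 / 0.5 = 13.2, with 2 and 108 degrees of freedom; power 0.904.
- N = 54: power 0.899.

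The smallest N is 55, as stated. Recruiting 60 allows 5/60 = 8.3% discontinuation. Acuity does not enter this calculation.

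**What is known, and when.** There are 60 × 3 = 180 subject-lens pairs.

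| Point in the plan | Lens types with acuity read, per subject | Pairs |
|---|---|---|
| Step 5, dispensing visit | 0 of 3 | 0 |
| End of dispensing visit | 1 of 3 | 60 (33%) |
| End of one-week visit | 2 of 3 | 120 (67%) |
| End of two-week visit | 3 of 3 | 180 |

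Step 2 does not say which correction is worn. If comparator wearers were tested in their habitual lens, at most 20 + 20 = 40 pairs (22%) would be known at step 5, and by design none for the Hydron lens. The count confirms the ordering problem. It does not show harm, because any crossover that dispenses lenses in sequence reads the later ones later.

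**Following the plan as written.** Acceptance at step 5 uses history, refraction and baseline acuity. None of these depends on the assigned order, so selection at entry cannot favour one lens over another. A subject who later sees poorly in one lens supplies an outcome for that lens.

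**If staff used step 7 instead.** The documents give no failure rates, SD or correlations, so everything here is assumed: normally distributed acuity with SD s = 0.10 logMAR, 20 subjects starting on each lens, and failures replaced within the same starting lens.

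Replacements at first fit = 20 × (pA + pB + pC):

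- 2% for each lens: 20 × 0.06 = 1.2
- 5% for each lens: 20 × 0.15 = 3.0
- 8% for each lens: 20 × 0.24 = 4.8

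Understatement of the A − B difference in mean acuity = (r − ρ) × s × (LA − LB)/3. Here L = φ(z)/(1 − p), r is the correlation between step 7 and follow-up readings in the same lens, and ρ is the correlation between lenses. L is 0.1616 at 8%, 0.1086 at 5% and 0.0494 at 2%.

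| Failure rates | r | ρ | Understatement (logMAR) |
|---|---|---|---|
| 8% v 2% | 1 | 0 | 0.10 × 0.1122/3 = 0.0037 |
| 8% v 2% | 0.9 | 0.5 | 0.4 × 0.0037 = 0.0015 |
| 8% v 2% | 0.8 | 0.8 | 0 |
| 5% v 2% | 1 | 0 | 0.10 × 0.0592/3 = 0.0020 |
| equal | any | any | 0 |

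The true difference implied by 8% against 2% is 0.0649, so the extreme case loses about 6% of it and the milder case about 2% (0.0015/0.0649). The extreme case needs zero correlation between lenses worn by the same eyes, which is not credible. The model also takes one acuity per subject, although the criterion is per eye.

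**The case for a change.** The strongest case for acting is that the contradiction is certain and rewording is cheap. The screening visit in section 2.1 does not rescue the text, since no lens fitting is described there and section 3.1 does not schedule it. Habitual wear of a comparator covers at most one lens per subject. An eligibility entry at step 5 cannot be checked against a lens reading, and the plan is silent on a subject below 6/9 in a later lens.

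All of that stands as a description of the wording. What does not follow is that the criterion is unusable. Section 2.1.3 also asks that subjects be able to wear the lenses for eight hours a day, which cannot be observed at step 5 either. Both can be read as the investigator's expectation.

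Nor is the obvious remedy free of cost. It would base step 5 explicitly on refraction acuity and bar replacement because of acuity in an assigned lens. The first part only writes down the data an investigator would already use, and good refraction acuity does not guarantee 6/9 in a lens. The second could leave up to 4.8 subjects unreplaced at the highest assumed rates. If they then supplied no data for that lens, 60 − 4.8 = 55.2 would remain against the required 55, nearly the whole margin. That would put comfort and preference data at risk to avoid a bias of at most 0.0037 logMAR in another measure. The available text breaks off where outcomes and analyses are listed, so the analytic role of acuity cannot be seen.

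**Conclusion.** The ordering conflict is real, but it calls for no change to the design or analysis. Followed as written, step 5 rests on information that does not depend on lens order, and the between-lens comparisons remain sound. Comfort (section 1.5), preference for attractiveness (section 1.5.1) and the sample size of 55 are not directly affected. Bias in the acuity comparison requires a departure from the written order together with unequal failure rates, and the documents support neither. Under the stated assumptions it ranges from 0 to 0.0037 logMAR.

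What remains is editorial: sections 2.1, 2.1.1, 2.1.3, 2.1.4, 2.2 and 3.2.1 must be reconciled on when, and in what correction, the acuity criterion is judged. How a subject below 6/9 in an assigned lens is managed is a clinical matter for that reconciliation; this review takes no position on it.

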3.2.2 One-week follow-up visit

Subjects should attend wearing the study lenses which should have been in situ for at least

two hours. Subjects who attend without lenses in situ for at least two hours will usually be rescheduled. The following procedures will be performed (any ocular measurement procedures outlined below will be carried out on each eye):

1. Lens wearing times since the previous visit will be recorded.

2. Lens wearing time on study visit day.

3. Monocular logMAR visual acuity (high contrast) with the study lens.

4. The subject will be asked to score the following qualities using a visual analog scale for:

Comfort after insertion

Comfort before removal

Orverall comfort	
Overall comfort	

7. The lenses will then be removed and discarded.

8. The investigator will then conduct a complete biomicroscopic examination of the clinical signs

9. The second pair of lenses will be applied

10. Visual acuity & lens fit will be assessed with second pair of lenses worn

3.2.3 Two and Three-week visit

Subjects should attend wearing the study lenses which should have been in situ for at least two hours. Subjects who attend without lenses in situ for at least two hours will usually be rescheduled. The following procedures will be performed (any ocular measurement procedures outlined below will be carried out on each eye):

1. The same procedures as the 1-week visit (3.2.2) sections 1-10 will be carried out.

2. Additionally, subjects will be asked to rank the lens in order of preference.

3. At the final visit (or when the subject is discontinued at an earlier visit) the subject will sign a study exit statement acknowledging that the work is complete, although they may have been asked by the investigator to attend a post-study follow-up visit, and that they should continue to use their lenses and solutions as advised, and seek aftercare for their contact lenses. A copy of this signed form will be issued to the subject.

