Clinical Investigation Plan

Study Title: Comparison of clinical performance and subjective preference out of three cosmetic contact lenses (limbal ring-enhancing lenses, LRE lenses)

SPONSOR: CooperVision Korea, Inc.

CLINICAL SITE: School of Optometry & Vision Science, Catholic University of

Daegu, Korea (Rep)

PROTOCOL DATE: October 21, 2016

PROPOSED START DATE: Dec, 2016

STUDY TITLE:

Comparison of clinical performance and subjective preference out of three cosmetic contact lenses (limbal ring-enhancing lenses, LRE lenses)

· · · ·

SPONSOR COMPANY: COOPERVISION KOREA, INC.

DOCUMENT TYPE: PROTOCOL

PRINCIPAL INVESTIGATOR:

DOCUMENT PREPARED BY:

DOCUMENT REVEIWED AND APPROVED BY:

Study summary

This bilateral subject-masked, randomized, crossover dispensing study will investigate the clinical performance **Control of the Hydron 1-day cosmetic contact lens** (Hydron Inc.), when compared to the 1-day Acuve Define (Johnson & Johnson Vision Care Inc.) and Claren 1-day Iris (Interrozzo Inc). Sixty subjects will be enrolled into this three-week study, where they will wear each lens type for one week. The order of lens wear will be randomized so that the effects related to order are minimized. The outcome measures will divided into subjective and objective measure. Primary subjective measure

Table 1: Study summary

Section 1. Overview

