1.4 Study Design

This will be a subject-masked if possible, bilateral, randomized, crossover dispensing study to compare clinical performance and subjective preference out of three lens types. Sixty subjects will be assigned into three groups and each group will wear the test and control lenses as matched pairs for one week each in random order. Lenses will be worn on a daily wear, daily disposable schedule.

Figure 1. Grouping and lens randomization order

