1.5 Statistical considerations

The prinicpal null hypothesis is that the comfort for the three lens types are equal. Prior to statistical analysis, normality of data will be assessed. Ordinal measure such as lens fit, biomicroscopy

Deviations from this

statistical plan will be discussed in the final report.

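### Does repeating the week-one steps at weeks two and three leave the third lens undispensed and the preference ranking undefined?

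*Combined protocol and SAP*

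**What the plan says.** Section 3.2.2 (one-week visit) has the worn lenses removed and discarded. Step 9 then says "The second pair of lenses will be applied", and step 10 says that visual acuity and "lens fit will be assessed with second pair of lenses worn". Section 3.2.3 covers both later visits under one heading: "The same procedures as the 1-week visit (3.2.2) sections 1-10 will be carried out". Its item 2 adds "Additionally, subjects will be asked to rank the lens in order of preference" and names no visit. Item 3, the exit statement, does name one: "At the final visit (or when the subject is discontinued at an earlier visit".

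The design text is firm on three lenses. The Study summary describes a three-week study "where they will wear each lens type for one week", and 1.4 says "each group will wear the test and control lenses as matched pairs for one week each in random order". Section 2.7 calls the study a controlled crossover with an assigned order. Section 3.1 schedules a dispensing visit and three follow-ups, and 3.2.1 fits the first lenses in randomised order. Section 1.5 mentions lens fit ("Ordinal measure such as lens fit, biomicroscopy"), but the public text of that sentence stops there.

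**The concern.** The cross-reference in 3.2.3 makes no substitution and no exception. Taken word for word, staff would reapply the second pair at week two, when the third is due, and apply it again at the exit visit, when no wear week remains. One of the three lenses would then never be dispensed or assessed for fit, although fit is named in 1.5. The crossover would in effect compare two lenses.

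The ranking looks loose for a related reason. By week two a subject has worn at most two lenses, so a ranking taken then covers one of the three pairings. If some subjects left after week two and their two-lens rankings were mixed with complete ones, mean ranks could shift. Section 3.4 allows partial datasets where appropriate, and no visible passage says which ranking is analysed.

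**Working it through.** **The plan's own figure.** Section 1.5.1 gives effect size 0.20 (taken as Cohen's f), alpha 0.05, one group, three repetitions, correlation 0.5 and power 0.90. For a within-subject repeated-measures ANOVA with sphericity assumed:

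- Noncentrality = n × m × f² / (1 − rho). At n = 55 this is 55 × 3 × 0.04 / 0.5 = 13.2, with 2 and 54 × 2 = 108 degrees of freedom.
- Power is 0.8986 at n = 54, 0.9043 at n = 55 and 0.9287 at n = 60.

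The smallest adequate n is 55, as stated. The calculation uses three repeated measures per subject, which agrees with three lenses worn by everyone.

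**Which pair is applied at each visit.**

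| Visit | Word for word | Implied by the Study summary, 1.4, 3.1 and 3.2.1 |
|---|---|---|
| Dispensing (3.2.1) | first | first |
| Week one (3.2.2) | second | second |
| Week two (3.2.3) | second | third |
| Week three (3.2.3) | second | none; wear is complete |

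The literal column has four applications, none of the third pair and one with no wear week left. It leaves uncovered 60 × 1 = 60 of the 60 × 3 = 180 planned subject-weeks. That column cannot be squared with the design: one lens type would be worn for two weeks and another for none. With three lenses, three wear weeks and a set order, only the right-hand column fits.

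**Lens fit.** The visible fit assessments are at application of the first pair (3.2.1, item 8) and of the second (3.2.2, step 10). Items 5 and 6 of 3.2.2 are absent from the public text. They fall after acuity and comfort scoring with the worn lens and before its removal. A fit check of the worn lens could sit there, and repeating the list would then cover every lens. This cannot be settled either way, so a missing fit assessment cannot be claimed.

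**Ranking.** Assume that all five allowed-for leavers (60 − 55) rank two lenses at week two, that these ranks are pooled with 55 complete rankings, and that there is no true preference, so each complete mean rank is 2.00.

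- *Balanced orders:* each lens has been worn by 5 × 2/3 = 3.33 leavers, with mean rank 1.5. The pooled mean is (55 × 2.00 + 3.33 × 1.5) / 58.33 = 1.97 for every lens, so there is no difference between lenses.
- *Extreme case:* all five wore the same lens and ranked it first. Its mean is (55 × 2.00 + 5 × 1) / 60 = 1.917, a shift of 0.083. The other lenses, ranked second by those who wore them, stay at 2.00.
- *Scale:* the null variance of a difference between two ranks from {1, 2, 3} is 2/3 + 2/3 + 2 × 1/3 = 2. The standard error of a difference in mean ranks with 55 subjects is √(2/55) = 0.191, and 0.083 / 0.191 = 0.44.

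**The case for a change.** The strongest reply is that a charitable reading mends only half the list. If the second pair is read as the next pair in the order, week two works, but week three still has an instruction with no pair left to apply. So no single reading of steps 9 and 10 suits both visits, and a case report form copied from the list could carry the error. The ranking item also sits under a joint heading beside an item expressly limited to the final visit, which makes a week-two ranking a natural reading.

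The wording fault stands: the cross-reference is careless and the ranking visit is unnamed. The consequence does not follow. At week three the subject signs that the work is complete, so a further application has no purpose and yields no outcome data. A week-two ranking, if taken, would be extra data and would not displace the complete one. The study title and 1.4 seek preference among three lens types, which only the week-three ranking can show. Section 3.4 also commits the report to giving the number of subjects in each analysis, so incomplete rankings would show in the counts.

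**Conclusion.** No change to the plan follows. Repeating steps 9 and 10 at the later visits is a clerical slip in a procedure list. The correct sequence follows directly from the Study summary, 1.4, 3.1 and 3.2.1, and rewording the list would alter nothing the trial does or concludes. The unnamed ranking visit is a gap that analysts fill sensibly, because a three-lens ranking exists only at week three. Even the unplanned pooling of five incomplete rankings gives at most 0.44 of a standard error, and no between-lens difference under balanced orders. The sample size is untouched.

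This rests on three assumptions: staff follow the randomised order and not the literal words second pair; early leavers number about the five allowed for; and the parts of 3.2.2, 1.5 and Figure 1 missing from the public text do not contradict the three-lens design. The possible gap in lens-fit data is left open because the text that would settle it cannot be seen.

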3.2.4 Post-study follow-up visit

In the case of a subject who exits the study with significant clinical signs or symptoms, the investigator must undertake to examine the subject at intervals he/she determines to be clinically appropriate until the sign or symptom has resolved or returned to a level that is considered to be clinically acceptable. Details from these visits will be recorded on a post study follow-up visit form.

